# 10.1.4. Secondary Efficacy Measures

Tumor response is defined by RECIST v1.1 (Eisenhauer et al. 2009) provided in Attachment 5. To derive the overall response rate, a responder is defined as any patient who exhibits a confirmed CR or PR. Best response is determined from the sequence of responses assessed.

A second assessment must be performed  $\geq 28$  days after the first evidence of response. The next scheduled scan at 56 days (8 weeks) would qualify for response confirmation. Two objective status determinations of CR before progression are required for a best response of CR. Two determinations of PR or better before progression, but not qualifying for a CR, are required for a best response of PR. Best response of SD is defined as disease that does not meet the criteria for CR, PR, or PD and has been evaluated at least 1 time, at least 6 weeks after the start of study treatment.

Best response will be derived to encompass all tumor assessments from baseline until the earliest of objective progression or start of new anticancer therapy. Any responses observed after objective progression or the start of new anticancer therapy are excluded from the determination of best response.

Progression-free survival will be defined as the time from randomization until the first evidence of objective progression as defined by RECIST v1.1 (Eisenhauer et al. 2009), or death from any cause, whichever is earlier. Patients who are not known to have either progressed or died at the time of analysis will be censored at the day of their last radiographic tumor assessment, if available, or the date of randomization if no postbaseline radiographic assessment is available. The detailed censoring rules are described in Table JPBK.12.2.

The PFS analysis will be based on the local investigator's tumor assessments.

The date of first documented objective disease progression must be recorded on the CRF even if it occurs after the patient has started a new therapy. Lilly or its designee will collect and store all tumor measurement images on all enrolled patients throughout the study. A central review of imaging scans may be performed by Lilly or its designee.

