# 5.2. Secondary Objectives

The secondary objectives of the study are to compare Abemaciclib plus BSC versus erlotinib plus BSC with respect to:

- Progression-free survival (PFS)
- overall response rate (complete response [CR] + partial response [PR]).
- changes in patient-reported pain and disease-related symptoms collected via the MD Anderson Symptom Inventory (MDASI-LC) and changes in health status via European Quality of Life – 5 Dimensions – 5 Level (EQ-5D-5L).
- safety and tolerability
- resource utilization (for example, analgesic type, hospitalization, transfusion)
- pharmacokinetic (PK) and pharmacodynamic (PD) properties of Abemaciclib

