# 6.2. Statistical and Analytical Plans

## 6.2.1. General Considerations

Statistical analysis of this study will be the responsibility of Lilly.

All tests of treatment effects will be conducted at a 2-sided alpha level of 0.05, unless otherwise stated. All tests of interactions will be conducted at a 2-sided alpha level of 0.1, and all confidence intervals (CIs) will be given at a 2-sided 95% level, unless otherwise stated. P-values will be rounded at three significant digits. P-values less than 0.001 will be presented as p <0.001.

Any change to the data analysis methods described in the protocol will require an amendment only if it changes a principal feature of the protocol.

Before unblinding of the aggregate database, minor modifications or clarifications to the data analysis methods may be described and justified in the statistical analysis plan (SAP).

Any other change to the data analysis methods described in the protocol, and the justification for making the change, will be described in the clinical study report.

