Best overall response (BOR) will be derived to encompass all tumor assessments (according to RECIST v1.1) from baseline until the earliest of objective progression or start of new anticancer therapy. Any responses observed after objective progression or the start of new anticancer therapy are excluded from the determination of best response. Each patient's BOR will categorized as complete response (CR), partial response (PR), stable disease (SD), progressive disease (PD), or not evaluable (NE).

Overall Response Rate (ORR) is defined as the proportion of patients with BOR of CR or PR (according to RECIST v1.1). Disease control rate (DCR) is defined as the proportion of patients with BOR of CR, PR or SD (according to RECIST v1.1).

Point estimates and 95% confidence intervals (using the normal approximation to the binomial) will be calculated for ORR and DCR by treatment arm. Stratified tests comparing these rates between treatment arms will be conducted using a Cochran-Mantel-Haenszel (CMH) test adjusted by all stratification factors.

Duration of response (DoR) will be presented for responders (patients with a BOR of CR or PR according to RECIST 1.1). DoR is defined as the time from the date of the first evidence of CR or PR to the date of investigator-determined objective progression or the date of death due to any cause, whichever is earlier. DoR will be censored according to the same rules as PFS (presented in Table JPBK.6.1). The median duration of response will be summarized using K-M

techniques. The statistical comparison of DoR between treatment groups will be conducted using unstratified log-rank test and HR will be estimated using an unstratified Cox model with only the treatment factor in the model.

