#### 6.2.10.4. Sensitivity Analyses

Sensitivity analyses may be undertaken in order to evaluate the robustness of the analysis.

**Restricted Mean Difference:** The common method for describing benefit on the time scale is to calculate the difference in median event time between the two treatment arms. An alternative method for describing benefit on the time scale is to estimate the average difference between the KM curves. This corresponds to calculating the difference in the average time to event for the two treatment arms (Irwin 1949; Karrison 1997; Meier et al. 2004). Similar to the HR, this method uses all of the available information across the KM curves, but has the additional advantage of assessing benefit on the time scale.

To estimate an improvement in OS with Abemaciclib, we will follow the method of Irwin (1949) detailed in Karrison (1997) and Meier (2004) for estimating the "difference in average OS", which we will refer to more formally as the restricted mean difference in OS. The area under each KM curve will be calculated using numerical integration (trapezium rule) per Karrison and implemented in SAS using PROC LIFETEST. The difference between treatment arms and a CI for the difference will be formed.

Since the KM curve may be ill-determined beyond a certain range, or even undefined (if the longest observation is censored), for evaluation and comparison of means, the area under each KM curve will be calculated between time 0 and restriction time T, which is why this is referred to as a "restricted mean". Following the suggestion of Karrison, the restriction time T will be chosen as largest time point t such that the standard error (SE) of the survival estimate at time t in each treatment group is no more than 0.075. For this purpose, we will use the simple, albeit conservative, formula proposed by Peto et al. (1977) for calculating the SE of S(t) as  $SE(S(t)) = S(t)\sqrt{(1-S(t))/n(t)}$ , where *n*(t) is the number of patients still at risk at time t. The following sensitivity analyses will be performed for OS:

**Overall Survival Sensitivity Analysis 1:** The comparison of the OS distributions between treatment groups will be conducted using a log-rank test without stratification factors as secondary analysis.

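### The SAP tests duration of response between arms among responders only, which is not a randomized comparison; it should be reported descriptively

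*SAP*

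**What the plan says.** SAP 6.2.10.3 defines the analysis set after randomization: "Duration of response (DoR) will be presented for responders", meaning patients whose best overall response is CR or PR. The clock starts at first response, not at randomization. After a Kaplan-Meier summary of the median, the section adds a formal comparison: "The statistical comparison of DoR between treatment groups will be conducted using unstratified log-rank test and HR will be estimated" from an unstratified Cox model containing treatment alone.

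Three other places bear on this.

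- SAP 6.2.1 sets the default level: "All tests of treatment effects will be conducted at a 2-sided alpha level of 0.05", unless the plan states otherwise. It states nothing else for DoR.
- SAP 6.2.2 assigns every efficacy analysis to the intent-to-treat population. A responder-only test does not fit that.
- The objectives in Protocol 6.2 and SAP 5.2 list response rate and PFS but not DoR. Protocol 10.1.4 and 12.2.7 plan no DoR comparison, and Attachment 5 only defines the measure. The between-arm test appears in the SAP alone.

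For the response rate in each arm, SAP 6.2.10.3 gives 95% intervals "using the normal approximation to the binomial". It compares the arms with a stratified Cochran-Mantel-Haenszel (CMH) test.

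**The concern.** Protocol 8.2 names randomization as the justification for inferential methods. That justification covers the 270 and 180 randomized patients. It does not cover whichever of them later respond. If abemaciclib changes who responds, the two responder groups differ in kind, and a difference in DoR mixes who responds with how long response lasts. A drug that brings brief responses to patients who would otherwise have had none can look worse on DoR. One that adds only long responses looks better on DoR even if it does not lengthen the responses that would have occurred anyway.

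At stake is a p-value and hazard ratio, listed under secondary efficacy endpoints, that would read as a treatment effect. The responder groups may also be small enough for the large-sample log-rank test, and the normal-approximation interval for the response rate, to be unreliable.

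**Working it through.** **Inputs from the documents.** 270 and 180 patients (SAP 6.1); responders only, unstratified log-rank test, treatment-only Cox model (SAP 6.2.10.3); two-sided 0.05 (SAP 6.2.1). The documents give no response rate or DoR. The Protocol introduction gives only disease control rates from the Phase 1 study.

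**The plan's own figure.** There is none for DoR. The OS figure reproduces: (1.96 + 0.8416)² / (0.6 × 0.4 × (ln 0.72)²) = 7.849 / 0.0259 = 303.05, rounded up to 304. It does not bear on this point.

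**Responders and power.** At an assumed 3% in both arms, 270 × 0.03 = 8.1 and 180 × 0.03 = 5.4, about 14 in total. At 10% there are 27 + 18 = 45. Power for a true DoR hazard ratio of 0.72, if every responder has an event, is Φ(√(d × 0.6 × 0.4) × 0.3285 − 1.96). With d = 13.5 this is Φ(0.591 − 1.96), about 9%. With d = 45 it is Φ(1.080 − 1.96), about 19%.

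**No treatment effect.** Simulating 270 versus 180 patients with exponential durations and no censoring, the log-rank test rejects in about 7.7% of trials at a 3% response rate and about 6% at 10%. The excess over 5% is a small-sample property of the test, separate from selection.

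**Selection.** Assume that 3% respond in either arm with a mean of 6 months, and that abemaciclib adds 3, 5 or 7 percentage points of responders with mean m. No patient does worse on abemaciclib. Its mean DoR is (0.03 × 6 + added × m) / (0.03 + added); the erlotinib mean is 6.

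| Added points | m (months) | Mean DoR, abemaciclib (months) | 6 / mean | Cox HR | Significant against / for abemaciclib |
|---|---|---|---|---|---|
| 3 | 3 | 4.5 | 1.33 | 1.31 | 6.9% / 1.9% |
| 5 | 3 | 4.125 | 1.45 | 1.42 | 9.2% / 1.6% |
| 7 | 3 | 3.9 | 1.54 | 1.49 | 11.3% / 1.2% |
| 5 | 6 | 6.0 | 1.00 | 1.00 | 1.8% / 5.8% |
| 3 | 9 | 7.5 | 0.80 | 0.81 | 0.7% / 9.7% |
| 5 | 9 | 7.875 | 0.76 | 0.77 | 0.4% / 11.6% |
| 7 | 9 | 8.1 | 0.74 | 0.75 | 0.2% / 13.5% |

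The 6-month row is the baseline. Even at a hazard ratio of 1.00, unequal and small groups give 5.8% significant in favour of abemaciclib. Roughly half of the 9-month rates is therefore small-sample imbalance, not selection.

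**A second mechanism.** Let prognosis drive both response and duration, with no treatment effect on duration. At 10% versus 10% the apparent hazard ratio is about 0.98. At 20% versus 10% it is 1.11 to 1.22, at 20% versus 5% it is 1.16 to 1.35, and at 10% versus 3% it is 1.08 to 1.21. The ranges run from moderate to strong dependence on prognosis.

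**Response-rate interval.** The Wald interval is p̂ ± 1.96 √(p̂(1 − p̂)/n). For 3/180, p̂ = 1.67% and the half-width is 1.96 × 0.954% = 1.87%, giving −0.2% to 3.5%; Clopper-Pearson gives 0.35% to 4.8%. The lower limit is negative whenever x < 3.84(1 − p̂), that is, at 1 to 3 responders. At none the interval is 0% to 0%. Exact coverage:

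| True rate | Wald, n = 180 | Wald, n = 270 |
|---|---|---|
| 1% | 83% | 93% |
| 2% | 87% | 90% |
| 3% | 90% | 90% |
| 5% | 94% | 92% |

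Clopper-Pearson coverage is 96% to 99% throughout.

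**The case against.** The strongest reply is that nothing depends on this test. DoR is not an objective, and neither the sample size nor the futility rule uses it. OS, PFS and response rate are all compared in the randomized arms. The 0.05 in SAP 6.2.1 is a default for every test and gives DoR no confirmatory standing. All of this is right, and it is why the point is minor. It does not rescue the test: if DoR is meant to be descriptive, the SAP should say so and should not ask for a p-value and hazard ratio.

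A second reply is that the sizes rest on invented inputs and that the direction follows from the assumed duration of the added responses. This also stands. The two mechanisms give different sizes, and neither estimates the bias in this trial. The structural point needs no numbers.

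A third is that the interval issue is separate and matters only at response rates of about 5% or below. That is fair, so it is kept as a minor companion. The interval method does not affect the SAP's CMH test. The same cannot be said of Protocol 12.2.7, which compares rates between arms by a normal approximation for the difference.

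**Conclusion.** The concern holds, with limited impact. As written, the SAP produces a DoR p-value and hazard ratio in groups selected by a post-randomization outcome. These are not a randomized comparison and can mislead in either direction. The sizes above are illustrations under assumed response rates, exponential durations and no censoring.

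Four stronger readings are tempting, and the documents do not support them.

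- A reader might infer that the trial's main conclusions or error rate are at risk. OS is the sole primary endpoint and does not use DoR.
- A reader might infer that the test is tilted towards or against abemaciclib. The documents give nothing from which to fix a direction.
- A reader might infer that responses need not be confirmed, because the SAP is silent and Attachment 5 carries generic text on randomized trials. Protocol 10.1.4 settles this: "a responder is defined as any patient who exhibits a confirmed CR or PR".
- A reader might infer that the SAP needs a replacement comparison, such as mean time in response over all randomized patients. Best response stops at new anticancer therapy while PFS in Table JPBK.6.1 does not, so that measure would need its own rule for later therapy. It would also need a workable restriction time. At an assumed 3% response rate and no effect, one version tried, with a fixed 12-month restriction, rejected 4.0% for abemaciclib and 1.3% against, where 2.5% a side is nominal. The response-rate and PFS comparisons already planned are enough.

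**What to change.** In SAP 6.2.10.3:

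(a) Delete the between-arm log-rank test and Cox hazard ratio for DoR. Report Kaplan-Meier DoR by arm, state that it is descriptive, and let the existing all-randomized comparisons of response rate and PFS carry the inference.

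(b) Minor: replace the normal-approximation interval for the response rate in each arm with Clopper-Pearson.

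The cost is SAP wording and minor programming. Part (a) gives up only a p-value and hazard ratio that randomization does not support, for a measure that is not a listed objective. Part (b) gives slightly wider intervals.

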#### 6.2.10.4. Sensitivity Analyses

Sensitivity analyses may be undertaken in order to evaluate the robustness of the analysis.

**Restricted Mean Difference:** The common method for describing benefit on the time scale is to calculate the difference in median event time between the two treatment arms. An alternative method for describing benefit on the time scale is to estimate the average difference between the KM curves. This corresponds to calculating the difference in the average time to event for the two treatment arms (Irwin 1949; Karrison 1997; Meier et al. 2004). Similar to the HR, this method uses all of the available information across the KM curves, but has the additional advantage of assessing benefit on the time scale.

To estimate an improvement in OS with Abemaciclib, we will follow the method of Irwin (1949) detailed in Karrison (1997) and Meier (2004) for estimating the "difference in average OS", which we will refer to more formally as the restricted mean difference in OS. The area under each KM curve will be calculated using numerical integration (trapezium rule) per Karrison and implemented in SAS using PROC LIFETEST. The difference between treatment arms and a CI for the difference will be formed.

Since the KM curve may be ill-determined beyond a certain range, or even undefined (if the longest observation is censored), for evaluation and comparison of means, the area under each KM curve will be calculated between time 0 and restriction time T, which is why this is referred to as a "restricted mean". Following the suggestion of Karrison, the restriction time T will be chosen as largest time point t such that the standard error (SE) of the survival estimate at time t in each treatment group is no more than 0.075. For this purpose, we will use the simple, albeit conservative, formula proposed by Peto et al. (1977) for calculating the SE of S(t) as  $SE(S(t)) = S(t)\sqrt{(1-S(t))/n(t)}$ , where *n*(t) is the number of patients still at risk at time t. The following sensitivity analyses will be performed for OS:

**Overall Survival Sensitivity Analysis 1:** The comparison of the OS distributions between treatment groups will be conducted using a log-rank test without stratification factors as secondary analysis.

**Overall Survival Sensitivity Analysis 2:** A stratified log-rank test with stratification factors the number of prior chemotherapy regimens (1 versus 2), ECOG PS (0 versus 1), and gender (male versus female) from eCRF, and *KRAS* mutation (G12C versus all others) from central lab will be conducted.

The following sensitivity analyses will be performed for PFS:

**Progression-Free Survival Sensitivity Analysis 1** (censoring for receiving subsequent systemic anticancer therapy): if a patient is initiated on another anticancer therapy prior to objective

progression including any postdiscontinuation treatment systemic therapy, PFS will be censored at the date of the last complete objective progression-free disease assessment before initiation of the new therapy, regardless of whether or not this patient subsequently had objective progression or died. The definition of PFS for this sensitivity analyses is presented in Table JPBK.6.2. Those items that differ from Table JPBK.6.1 are underlined.

**Progression-Free Survival Sensitivity Analysis 2** (nonobjective progression as a PFS event): if a patient is discontinued from study treatment due to investigator determined non-objective progression (for example, symptomatic deterioration), then the patient's PFS time will be calculated using the date of non-objective progression as the progression date. The definition of PFS for this sensitivity analyses is presented in Table JPBK.6.3. Those items that differ from Table JPBK.6.1 are underlined.

**Progression-Free Survival Sensitivity Analysis 3** (forward-dating progressions at unscheduled assessments): if a patient has objective progression at an unscheduled disease assessment, then the PFS time for that patient will be forward-dated to the next scheduled disease assessment. The definition of PFS for this sensitivity analyses is presented in Table JPBK.6.4. Those items that differ from Table JPBK.6.1 are underlined.

	Situation	Date of Progression or Censor	Outcome
1	No baseline tumor assessments	Date of Randomization	Censored
2	No post baseline assessments and no death	Date of Randomization	Censored
3	No documented progression and no death (with a post-baseline tumor assessment)	Date of last adequate tumor assessment	Censored
4	Patient lost to follow-up (or withdrew consent from study participation) before documented progression or death	Date of last adequate tumor assessment	Censored
5	Documented progression	Date of documented progression. If a tumor assessment was done on multiple days, use the earliest date for that visit.	Progressed
6	Death without documented progression	Date of death	Progressed
7	Death or documented progression immediately after missed ≥2 consecutive post-baseline tumor assessment visits	Date of last adequate tumor assessment before missed assessments or date of randomization, whichever is later	Censored
8	New anticancer treatment started	last complete objective progression-free disease assessment before initiation of the new therapy	Censored

#### Table JPBK.6.2. Progression-Free Survival Sensitivity Analysis 1

Note: PFS and associated outcome is determined by the earliest of the dates above, if more than one situation applies

	Situation	Date of Progression or Censor	Outcome
1	No baseline tumor assessments	Date of Randomization	Censored
2	No post baseline assessments and no death	Date of Randomization	Censored
3	No documented progression and no death (with a post-baseline tumor assessment)	Date of last adequate tumor assessment	Censored
4	Patient lost to follow-up (or withdrew consent from study participation) before documented progression or death	Date of last adequate tumor assessment	Censored
5	Documented progression	Date of documented progression. If a tumor assessment was done on multiple days, use the earliest date for that visit.	Progressed
6	Death without documented progression	Date of death	Progressed
7	Death or documented progression immediately after missed ≥2 consecutive post-baseline tumor assessment visits	Date of last adequate tumor assessment before missed assessments or date of randomization, whichever is later	Censored
8	Investigator determined non-objective progression	Date of non-objective progression	Progressed

#### Table JPBK.6.3. Progression-Free Survival Sensitivity Analysis 2

Note: PFS and associated outcome is determined by the earliest of the dates above, if more than one situation applies

#### Table JPBK.6.4. Progression-Free Survival Sensitivity Analysis 3

	Situation	Date of Progression or Censor	Outcome
1	No baseline tumor assessments	Date of Randomization	Censored
2	No post baseline assessments and no death	Date of Randomization	Censored
3	No documented progression and no death (with a post-baseline tumor assessment)	Date of last adequate tumor assessment	Censored
4	Patient lost to follow-up (or withdrew consent from study participation) before documented progression or death	Date of last adequate tumor assessment	Censored
5	Documented progression	Date of documented progression. If a tumor assessment was done on multiple days, use the earliest date for that visit.	Progressed
6	Death without documented progression	Date of death	Progressed
7	Death or documented progression immediately after missed ≥2 consecutive post-baseline tumor assessment visits	Date of last adequate tumor assessment before missed assessments or date of randomization, whichever is later	Censored
8	Objective progression at an unscheduled disease assessment	Date of next scheduled disease assessment.	Progressed

Note: PFS and associated outcome is determined by the earliest of the dates above, if more than one situation applies

Additional sensitivity analyses for OS and PFS may be carried out for patients who are *KRAS* positive based only on central test result. Patients who are enrolled with their *KRAS* mutation status based only on local lab reported in the eCRF are excluded in these analyses. For these analyses, the statistical analysis model described in Section 6.2.10.2 will be applied.

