#### 7.1. Inclusion Criteria

Patients are eligible to be included in the study only if they meet **all** of the following criteria:

- [1] have confirmed diagnosis of stage IV NSCLC according to the American Joint Committee on Cancer Staging Handbook (Edge et al. 2009).
- [2] have availability of adequate FFPE tumor-derived material (tumor blocks or slides) from a biopsy, surgery or fine needle aspirate for analysis of *KRAS* mutation status. This sample should be the most recent available sample containing adequate material. Tumor sample requirements are described in Section 10.4.2.1. The sponsor will not request re-biopsy solely for the purpose of testing of *KRAS* status.
  - [2A] For patients who do not have adequate FFPE tumor-derived material for *KRAS* mutation status analysis, eligibility may be considered based upon a local

*KRAS* mutation result as described in Section 10.4.2.2. The sponsor will not request re-biopsy solely for the purpose of testing of *KRAS* status.

- [3] determined to have detectable mutations in codons 12 or 13 of the *KRAS* oncogene by an investigational assay at the Study JPBK central laboratory
  - [3A] A *KRAS* positive mutation result in codons 12 or 13 of the *KRAS* oncogene from tumor tissue per local laboratory will be permitted in no more than 10% of the randomized patients; thus, requirement of a central laboratory *KRAS* positive mutation result is waived. No serum or plasma *KRAS* mutation results are permitted for consideration.
- [4] have progressed after platinum-based chemotherapy (with or without maintenance therapy [see below]) AND have received 1 additional therapy which may include an immune checkpoint inhibitor or other anti-cancer therapy for advanced and/or metastatic disease; OR is judged by the physician as ineligible for further standard second-line chemotherapy. Patients who have progressed after platinum-based chemotherapy and an immune checkpoint inhibitor (immunotherapy) e.g. pembrolizumab or nivolumab alone or in combination with other agents are eligible.

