#### 10.4.2.2. Local Laboratory Result

Local *KRAS* testing is not mandatory or considered a protocol required procedure. To address the challenges identified with tissue for *KRAS* testing by the central laboratory, a local *KRAS* mutation result from tumor tissue may be used for patient eligibility for no more than 10% of the randomized patients. These patients, who have a positive local *KRAS* result for one of the 7 specific mutations listed below, will be allowed to enter into the study with this result in the absence of a central laboratory *KRAS* positive result. Instructions will be provided by the sponsor to request approval to use a local *KRAS* mutation result for patient eligibility. The sponsor will review each request and provide approval to the site prior to the patient being randomized. Once approved and randomized to study using local laboratory *KRAS* result, no additional tumor tissue should be submitted to the central laboratory for *KRAS* testing.

In order for a patient with a local *KRAS* mutation result to be considered eligible, the following circumstances must be present:

(a) The local *KRAS* mutation result is one of the following mutations:

- G12A (35G>C) (GLY12ALA)
- G12S (34G>A) (GLY12SER)
- G12D (35G>A) (GLY12ASP)
- G12R (34G>C) (GLY12ARG)
- G12C (34G>T (GLY12CYS)
- G12V (35G>T) (GLY12VAL)
- G13D (38G>A) (GLY13ASP)

(b) The reason for the request for approval to use local *KRAS* mutation test result for inclusion is due to one or more of the following:

• No tissue available for submission to Study JPBK central laboratory that has a documented confirmation by the investigator

- Indeterminate designation obtained from initial sample submitted to Study JPBK central laboratory
- An inadequate sample designation (for example, Insufficient Tissue Received at Laboratory, No Neoplastic Cells in Tissue) obtained from initial sample submitted to Study JPBK central laboratory

Once enrollment of no more than 10% of randomized patients has been reached, the sponsor will communicate that enrollment by local *KRAS* mutation result has been suspended. No additional patients will be randomized using local *KRAS* mutation results.

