# 4. Study Design

Study I3Y-MC-JPBK is a multicenter, randomized, open-label, parallel, comparator-controlled trial in patients with Stage IV NSCLC whose tumors have a detectable KRAS mutation in codons 12 or 13 by an investigational assay at the Study JPBK central laboratory and who have progressed after platinum-based chemotherapy and received 1 other prior therapy or are ineligible for further chemotherapy after platinum-based therapy.

Figure JPBK.4.1 illustrates the study design.

Abbreviations: ECOG = Eastern Cooperative Oncology Group; NSCLC = non-small cell lung cancer; PD = progressive disease; PO = orally; Q12H = every 12 hours; Q24H = every 24 hours; PS = performance status.

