## 6.2.2. Populations

The entered population includes all patients who sign the informed consent document.

The **enrolled or intent-to-treat (ITT)** population includes all randomized patients. The ITT analysis of efficacy data will consider allocation of patients to treatment groups as randomized and not by actual treatment received. This population will be used for all baseline, efficacy, and health economics analyses.

**Safety population** will include all randomized patients who received any quantity of study treatment, regardless of their eligibility for the study. The safety evaluation will be performed based on the first dose of study treatment a patient actually received, regardless of the arm to which he or she was randomized. The safety population will be used for all dosing/exposure, safety, and resource utilization analyses.

Pharmacokinetic analyses will be conducted on all patients who have received at least 1 dose of Abemaciclib and have had samples collected.

Pharmacodynamic and/or tailoring biomarker analyses will be based on the subset of patients from the above populations from whom a valid assay result (according to laboratory guideline) has been obtained.

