# 6.2.4. Handling of Dropouts or Missing Data

With the exception of dates, missing data will not be imputed. The method of imputation for any dates that are imputed is described in the relevant section.

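### Does OS Sensitivity Analysis 2 drop patients enrolled on a local KRAS result, because it takes the KRAS stratum from the central laboratory?

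*SAP*

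**What the plan says.** **Sensitivity analysis.** SAP 6.2.10.4 defines OS Sensitivity Analysis 2 as a stratified log-rank test. Number of prior chemotherapy regimens, ECOG performance status and gender come from the eCRF. The KRAS factor is specified by the words "mutation (G12C versus all others) from central lab will be conducted". No second source is named.

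**Local route.** Under Protocol 7.1, criterion [3A], a positive local tumor-tissue result "will be permitted in no more than 10% of the randomized patients". Protocol 10.4.2.2 limits this route to one of seven named mutations and to three situations: no tissue for the central laboratory, an indeterminate central result, or an inadequate sample. The sponsor must review each request and "provide approval to the site prior to the patient being randomized". Once such a patient is randomized, "no additional tumor tissue should be submitted to the central laboratory" for KRAS testing.

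**General rules.** SAP 6.2.2 says of the ITT population, which is all randomized patients: "This population will be used for all baseline, efficacy, and health economics analyses". SAP 6.2.4 says: "With the exception of dates, missing data will not be imputed". SAP 6.2.10.1 makes the IWRS the default source of strata unless something else is stated. It adds that the factors are held in both the IWRS and the eCRF, with KRAS status also held by the central laboratory system.

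**Primary test.** SAP 6.2.10.2 takes all four strata from the IWRS.

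**The concern.** A stratified log-rank test needs a stratum for every patient. None of the three situations that open the local route yields a central G12C/other value, and later central testing is ruled out. The missing value is therefore built into the design for this group. The analysis names the central laboratory as its source, which seems to switch off the IWRS default, and the SAP imputes nothing but dates. Taken at face value, these patients would be omitted, against the ITT rule.

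The purpose of the analysis makes this look worse. It appears meant to show whether the OS result depends on where the strata come from. If the local-route patients drop out, the population changes along with the source, and a difference from the primary result could not be put down to the strata alone. The central-only analysis on IWRS strata, which could separate the two effects, is optional.

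Other parts of the SAP suggest that the local route was not carried through everywhere. Section 4 still describes the patients as having a "detectable KRAS mutation in codons 12 or 13 by an investigational assay at the Study JPBK central laboratory", and the KRAS inconsistency check in 6.2.17 compares the IWRS only with the central laboratory.

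**Working it through.** **1. Who lacks a central value, and what is recorded for them**

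| Source | Local-route patient | Where the documents say so |
|---|---|---|
| Central laboratory | normally no G12C/other value | Protocol 10.4.2.2 |
| IWRS | should have a KRAS stratum: randomization runs separately in 16 cells, and G12C versus others is one of the four factors | Protocol, randomization text before Section 9.4; SAP 6.2.10.1 |
| eCRF | local KRAS status is recorded, and the result must be one of seven named mutations, so G12C status is known | SAP 6.2.10.4, last paragraph; Protocol 10.4.2.2 |

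The local result is approved before randomization and KRAS is a randomization factor. The IWRS and eCRF values should therefore agree except for entry errors.

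**2. Possible readings, tested against the SAP's own rules**

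- *Use the IWRS value.* This respects the ITT rule. The default gives way only where another source is stated, and for a patient with no central value the analysis in effect states none.
- *Use the local result in the eCRF.* This respects the ITT rule and fits an analysis that already takes its other three strata from the eCRF.
- *Omit the patient.* This breaks the ITT rule. SAP 6.2.4 does not force it, because using a value already recorded in another study system is not imputation. Where the SAP wants local-only patients out, it says so, and only for the optional central-only analyses at the end of 6.2.10.4.

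Two readings keep everyone in and should give the same strata. The third conflicts with a general rule and has no sentence of its own to support it.

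**3. Size if the patients were omitted anyway**

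The plan's own figure first. Inputs from SAP 6.1: HR 0.72, 3:2 allocation (share 0.6), two-sided alpha 0.05, power 80%. Schoenfeld's formula gives

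d = (1.960 + 0.842)² / [0.6 × 0.4 × (ln 0.72)²] = 7.85 / (0.24 × 0.1079) ≈ 303.1, rounded up to 304.

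Power at 304 deaths is Φ(√(304 × 0.24 × 0.1079) − 1.960) = Φ(0.846) = 80.1%. The stated design reproduces.

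The documents do not give the actual local share, so a range up to the cap is assumed, with deaths lost in proportion to patients:

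| Local share | Patients (of 450) | Deaths lost (of 304) | Deaths left | Power at HR 0.72 |
|---|---|---|---|---|
| 0% | 0 | 0 | 304 | 80.1% |
| 2% | 9 | 6.1 | 297.9 | 79.3% |
| 5% | 22.5 | 15.2 | 288.8 | 78.1% |
| 10% (cap) | 45 | 30.4 | 273.6 | 75.9% |

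The power column only shows how little information is at stake; the study is not powered on this analysis. At the cap, the standard error of the log hazard ratio grows by a factor 1/√0.9 = 1.054, or about 5%. The local route opened only with amendment (c), approved on 16 June 2016, against a planned first visit in September 2014. The share may therefore lie below the cap.

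**4. Direction**

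Entry by the local route is settled before randomization. Leaving these patients out would remove a group defined at baseline, so the remaining comparison is still randomized. Information is lost, but no bias between arms is introduced.

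**The case for a change.** The strongest case for a change is that a plan should not leave the source of a stratum to the programmer, and that even a small omission can move a borderline p-value. Suppose the test on all patients gives Z = 1.960 (p = 0.050). After random loss of a share s, the statistic has mean √(1 − s) × 1.960 and standard deviation √s. At s = 0.10 the mean is 1.859 and the SD 0.316. The 95% range of Z is then 1.240 to 2.479, that is p from 0.215 to 0.013. At 5% the range of p is 0.019 to 0.141, and at 2% it is 0.027 to 0.096. A reader could take such a shift for sensitivity to the strata. One sentence would prevent it, and the SAP allows clarifications of that kind before unblinding.

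It stands that the source is unstated and that a sentence would be cheap. The illustration carries less weight. It needs three things at once: omission against the ITT rule, an all-patient result exactly at 0.050, and, for the widest range, a full 10% cap. It shows that random deletion moves a borderline result in either direction, which is true of any deletion, and no decision in the plan rests on this p-value.

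The two supporting points are weaker. SAP Section 4 is descriptive text that has lagged behind the local route and sets no analysis rule. The check in 6.2.17 covers violations that can be derived from the data. A patient with no central value offers nothing to compare and is dropped from no analysis.

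**Conclusion.** No change follows. The SAP leaves out one detail: which recorded source gives the KRAS stratum in OS Sensitivity Analysis 2 when there is no central result. The ITT rule says these patients stay in, the data to place them should exist in two systems, and those two should agree. An analyst would fill the gap sensibly, and naming the source in a table footnote is ordinary reporting practice.

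If the narrow reading were applied, the loss would be at most about 45 of 450 patients and about 30 of 304 deaths, confined to one supportive test and without bias between arms. The primary OS test on IWRS strata, its type I error and the unstratified OS Sensitivity Analysis 1 would be untouched, so the trial's conclusion would not depend on the choice.

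This rests on three assumptions: the 10% cap is observed, deaths fall in proportion to patients, and the IWRS holds a KRAS stratum for every randomized patient, as the randomization scheme requires.
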